## 10.0 Safety Analyses

### 10.1 General Considerations

Safety data will be summarized for the Safety Population. Safety summaries will be presented by treatment group, including a total group for all subjects on active study drug.

For the safety analysis, subjects are assigned to a treatment group based on the treatment actually received, regardless of the treatment randomized.

A subject's actual treatment will be determined by the most frequent dose regimen received.

"Baseline" refers to the last non-missing observation on or before the day of the first administration of study drug or randomization if no study drug is given. Observation on the same day as the first administration of study drug will be considered for the baseline, regardless if observation time (if available) was after the first administration of study drug time.

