5.8 Study Drug

ABBV-154 and Matching Placebo

ABBV-154 and matching placebo will be manufactured and provided by AbbVie (Table 1). Each dose will be administered by a healthcare professional as 3 SC injections (2 prefilled syringes [PFS] with 1.5 mL fill volume and 1 PFS with 0.4 mL fill volume) in the abdomen or thigh. Blinded study drug will be administered EOW at approximately the same time of day, preferably between 7 and 11 a.m., beginning on Day 1 (Baseline Visit). The study drug can be taken with or without food. A 15- to 30-minute observation period is required after each dose. The last dose of ABBV-154/placebo will be given at Week 50.

ABBV-154 and matching placebo syringes will be packaged in cartons with quantities sufficient to accommodate the study design. Each prefilled syringe and carton will be labeled per local requirements and these labels must remain affixed to the syringe and carton. Upon receipt, study drug should be stored as specified on the label (refrigerated at 2 to 8°C) and kept in a secure location. Each kit will contain a unique kit number. This kit number is assigned to a subject via Interactive response technology (IRT) and encodes the appropriate study drug to be dispensed at the subject's corresponding study visit. Study drug must not be dispensed without contacting the IRT system. Site staff will complete all blank spaces on the label before dispensing study drug for the subject. Study drug is for investigational use only and will only be used for the conduct of this study.

Table 1. Investigational Product

Study Drug	Dosage Form	Strength	Route of Administration	Manufacturer
ABBV-154	Solution for Injection/infusion in PFS	40 mg 150 mg	subcutaneous	AbbVie
Placebo for ABBV-154	Solution for Injection/infusion in PFS	Not applicable	subcutaneous	AbbVie

PFS = prefilled syringe

Glucocorticoids

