## **9.0 Efficacy Analyses**

### **9.1 General Considerations**

All efficacy analyses will be conducted in the ITT Population in each period. In addition, Per-protocol analysis for the primary endpoint will be performed. All tests will be 2-sided at an alpha level of 0.1.

The Primary Analysis will be performed after all subjects have either completed the Week 24 visit or withdrawn from the study. This analysis will be the only and final analysis for the primary and secondary efficacy endpoints.

The primary endpoint will be analyzed using logrank test stratified by baseline stratification factors [Glucocorticoid use at Baseline ( $\geq 10$  mg/day;  $< 10$  mg/day prednisone equivalent); Length of prior glucocorticoid treatment for PMR ( $\leq 1$  year;  $> 1$  year)]. The point and 95% confidence interval (CI) estimate of median time to event and event-free rate for each group will be reported based on Kaplan-Meier curves. Hazard ratio and its corresponding 95% CI for each ABBV-154 group compared with placebo will be estimated using Cox regression analysis adjusting for Baseline stratification factors [Glucocorticoid use at Baseline ( $\geq 10$  mg/day;  $< 10$  mg/day prednisone equivalent); Length of prior glucocorticoid treatment for PMR ( $\leq 1$  year;  $> 1$  year)]. For all analyses of time-to-event endpoints, 1) subject without an event at the time of the analysis will be administratively censored at the time of the last available assessment or cutoff, whichever is later; 2) a flare at Baseline will not be counted as an event; 3) if a flare event and an intercurrent event happen on the same day, subject will be counted as having a flare event.

Unless otherwise specified, the categorical endpoints and continuous endpoints will be analyzed by Cochran-Mantel-Haenszel (CMH) and Mixed-Effect Model Repeat

Measurement (MMRM), respectively, and the corresponding analyses are specified in Section 9.2.

Unless otherwise specified, any subject who is randomized based on a wrong stratum will be analyzed according to the actual stratum the subject belongs to.

"Baseline" refers to the last non-missing observation on or before the day of the first administration of study drug or randomization if no study drug is given. Observation on the same day as the first administration of study drug will be considered for the baseline, regardless of whether observation time (if available) was before or after the first administration of study drug time.

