### **10.2.1 Treatment-Emergent Adverse Events**

Treatment-emergent AEs are defined as any AE with the onset that is after the first dose of study drug and with an onset date no more than 5 half-lives of the study drug (i.e., 70 days). Events where the onset date is the same as the study drug start date are assumed to be treatment-emergent, unless the study drug start time and the AE start time are collected and the AE start time is prior to the study drug start time. All treatment-emergent AEs will be summarized overall, as well as by primary MedDRA SOC and Preferred Term. The SOCs will be presented in alphabetical order, and the PTs will be presented in alphabetical order within each SOC.

The number and percentage of subjects experiencing treatment-emergent AEs will be summarized.

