### 10.3 Analysis of Laboratory Data

Data collected from central and local laboratories, including additional laboratory testing due to an SAE, will be used in all analyses, except for Baseline where SAE-related laboratory assessments on or before the first dose of study drug will be excluded. The clinical laboratory tests defined in the protocol operations manual (e.g., hematology and clinical chemistry) will be summarized.

Each laboratory variable will be summarized for all time points (starting with Baseline) with the number of non-missing observations, mean and standard deviation, median, minimum and maximum. Mean change from baseline to each applicable post-baseline visit will be summarized for selected laboratory variables, with the number of observations, baseline mean, and visit mean. The change from baseline mean, standard error, and 95% confidence interval will be presented for the mean change from baseline within each treatment group and difference between treatment groups (ABBV-154 vs. placebo).

Changes in laboratory parameters will be tabulated using shift tables either by NCI CTC criteria or categorized as low, normal, or high based on the normal ranges of the laboratory used for each sample. A shift table from baseline either to the worse value (based on NCI CTC criteria) during treatment or to minimum and maximum value (based on normal range), will be created. A similar shift table will be provided to summarize shifts from baseline to the final post-baseline value.

Laboratory abnormalities meeting CTC criteria grade 3 and 4 will be summarized.

Laboratory abnormalities will be evaluated based on Potentially Clinically Important (PCI) criteria (criteria in PSSAP will be used first, if the criteria are not available in PSSAP, then criteria in NCI CTC will be used). For each laboratory PCI criterion, the number and percentage of subjects who have a laboratory value meeting the criteria will be summarized. Listings will be provided to summarize subject-level laboratory data for subjects meeting PCI criteria.

For the purpose of assessing for potential Hy's law cases, the frequencies and percentages of subjects with post baseline liver specific function test values that meet the following criteria of potential clinical interest will be summarized by "as treated" treatment group:

- $ALT > 3 \times ULN$
- $ALT > 5 \times ULN$
- $ALT > 10 \times ULN$
- $ALT > 20 \times ULN$
- $AST > 3 \times ULN$
- $AST > 5 \times ULN$
- $AST > 10 \times ULN$

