#### **10.4 Analysis of Vital Signs**

Vital sign measurements of systolic and diastolic blood pressure, pulse rate, respiratory rate, and body temperature will be summarized.

Each vital sign variable will be summarized for all time points (starting with Baseline) with the number of non-missing observations, mean and standard deviation, median, minimum and maximum. Mean change from baseline to each applicable post-baseline visit will be summarized for each vital sign variable, with the number of observations, baseline mean, and visit mean. The change from baseline mean, standard error, and 95%

confidence interval will be presented for the mean change from baseline within each treatment group and difference between treatment groups (ABBV-154 vs. Placebo).

Vital sign variables will be evaluated based on PCI criteria. Pulse rate, body temperature, and respiratory rate will follow the criteria in Appendix B. All other vital sign measurements will follow criteria in PSSAP. For each vital sign PCI criterion, the number and percentage of subjects who have a vital sign value meeting the criteria will be summarized. Listings will be provided to summarize subject-level vital sign data for subjects meeting PCI criteria.

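### The safety Baseline rule in SAP 10.1 lets a timed post-dose Day 1 repeat replace the pre-dose value, which distorts that subject's later change, shift and pulse PCI results

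*SAP*

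**What the plan says.** **Safety Baseline.** SAP 10.1 says: "Baseline' refers to the last non-missing observation on or before the day of the first administration of study drug". It then admits any observation made on the first-dose day "regardless if observation time (if available) was after the first administration of study drug time". SAP 9.1 has the same convention for efficacy ("regardless of whether observation time (if available) was before or after the first administration of study drug time"). The SAP version history (14.0) lists the Baseline definitions in both sections among the version 2.0 additions, so the wording is deliberate.

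**Same-day adverse events.** SAP 10.2.1 does use the clock. An event starting on the first-dose day is taken as treatment-emergent, with this exception: "unless the study drug start time and the AE start time are collected and the AE start time is prior to the study drug start".

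**Where safety Baseline is used.**
- SAP 10.3, shift tables: "A shift table from baseline either to the worse value (based on NCI CTC criteria) during treatment". The liver-test thresholds in the same section count post-baseline values.
- SAP 10.4: "Mean change from baseline to each applicable post-baseline visit will be summarized for each vital sign variable".
- SAP Table B2: high pulse needs at least 120 bpm and a rise of at least 15 from Baseline. Low pulse needs at most 50 bpm and a fall of at least 15.

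**The only exception.** SAP 10.3 uses laboratory data prompted by an SAE in all analyses, "except for Baseline where SAE-related laboratory assessments on or before the first dose of study drug will be excluded". Vital signs have no such exception.

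**Setting.** The first dose is given at the Baseline Visit. Protocol 5.8 states: "A 15- to 30-minute observation period is required after each dose".

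**The concern.** A Baseline should describe the subject before exposure. Here, when pre-dose and post-dose Day 1 values of one parameter both exist, the word last selects the post-dose one, even where the recorded times show the order.

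The subjects most likely to have such repeats are those who became unwell after the first injection. Protocol 2.2 names serious allergic reactions, including anaphylaxis, among the risks of TNF antagonists, and Protocol 6.2 asks for a serum sample within 2 hours, and no later than 6 hours, of the onset of a suspected systemic reaction. One episode could then be a treatment-emergent event in the AE tables while the measurements taken during it serve as Baseline in the laboratory and vital-sign tables. At stake is the measurement evidence for that subject: the reaction values stop counting as post-baseline, and every later comparison starts from a disturbed value.

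**Working it through.** No design figure is involved, so there is nothing in the plan to reproduce. The check applies the Baseline rule and the Table B2 pulse criteria to illustrative readings, which are assumptions and not trial data.

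**Formula.** Change = value − Baseline. High flag: value ≥ 120 and change ≥ +15. Low flag: value ≤ 50 and change ≤ −15.

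**Case A: a masked flag.** Pre-dose 80, post-dose Day 1 130, Week 1 80, a later visit 125.

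| Reading | Pre-dose Baseline (80) | SAP 10.1 Baseline (130) |
|---|---|---|
| Day 1 post-dose, 130 | 130 − 80 = +50, high flag | 130 − 130 = 0, no flag |
| Week 1, 80 | 80 − 80 = 0, no flag | 80 − 130 = −50, no flag |
| Later, 125 | 125 − 80 = +45, high flag | 125 − 130 = −5, no flag |

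**Case B: a false flag.** Pre-dose 60, post-dose Day 1 130, a later visit 50. With the pre-dose Baseline, 50 − 60 = −10, so there is no low flag. Under SAP 10.1, 50 − 130 = −80, so the low flag is raised.

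**Effect on an arm mean.** In Case A every later change for that subject is 50 bpm too low. With the planned 40 subjects per arm all contributing, one such subject moves the arm's mean change by −50 / 40 = −1.25 bpm at each later visit.

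**Shift tables.** The same logic applies to a laboratory grade. If the post-dose sample carries a raised grade, that grade becomes the starting category. A later return to normal reads as improvement, and a later recurrence at the same grade reads as no shift.

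**Does the 10.3 exception help?** It covers SAE-related laboratory values up to the first dose. A sample drawn hours after the dose on the same day is not clearly covered. Laboratory repeats not tied to an SAE, and all vital signs, lie outside it.

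**Can the trigger occur?** The Activity Schedule (Protocol Appendix F) shows one Baseline collection of vital signs, hematology and chemistry. It marks the PK and anti-drug-antibody samples as predose but not these safety measures. The trigger is therefore an unscheduled repeat, which the post-dose observation period makes possible but does not require.

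**The case against.** The strongest reply is that the rule rarely bites and that a simple time cut-off would do harm.

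- **Rarity.** No post-dose Day 1 safety measurement is scheduled, and the observation period requires none. The serum sample in Protocol 6.2 is for hypersensitivity tests listed in the Operations Manual, which was not available and may also fix the order of procedures. Nothing available shows that this sample feeds the routine laboratory tables. This stands, and it limits the size of the point.
- **Loss of Baseline.** The lipid profile is collected at Baseline but not at Screening. Where a Screening value does exist, it may be up to 35 days old and come from a time when the subject was on a higher prednisone dose. A strict cut-off would cost some subjects their Baseline or replace it with a stale one. This also stands, and the fix must allow for it.
- **Different derivations.** AE timing and measurement Baseline are separate rules, and different same-day conventions are not by themselves a contradiction. That is fair. The defect is that a value known to be post-dose displaces a pre-dose value that exists.

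A reader might infer more than the documents support:

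- *That first-dose reactions are hidden.* They are not. SAP 10.2.1 counts them as treatment-emergent, and they pass to the SAE, discontinuation and special-interest summaries where they qualify.
- *That all PCI tables are affected.* Only the pulse criteria visibly depend on Baseline. Temperature, respiratory rate, HbA1c, HDL and LDL use absolute thresholds, and SAP 10.4 does not limit vital-sign PCI counts to post-baseline values. Other criteria are in a product-level safety plan that was not available.
- *That the active arms are favoured.* No source supports this. The trial is double-blind, and the observation period applies to every dose in every arm.
- *That SAP 9.1 needs the same change.* HAQ-DI, pain, morning stiffness, Physician Global and upper-limb elevation are collected at Baseline with no Screening value, and the daily diary starts on Day 1. The only Day 1 value may be timed after dosing, and the MMRM needs a Baseline as covariate. The first-dose-reaction argument concerns safety measures.

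**Conclusion.** The point holds, with minor severity. Whenever a subject has both a pre-dose value and a later timed post-dose value of the same safety parameter on Day 1, SAP 10.1 gives the wrong Baseline, and no other text in the two documents corrects it. The result is distorted later changes and shifts for that subject and, for pulse, flags that may be masked or false.

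The number affected is probably small and cannot be estimated from the documents. The pulse readings show the mechanism, not its frequency. What is at risk is the laboratory and vital-sign record around a first-dose event, not the capture of the event itself. The conclusion assumes that at least some unscheduled Day 1 repeats are entered with times and that the Operations Manual does not already exclude them from Baseline.

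**What to change.** **SAP 10.1.** When the observation time and the first-dose time are both recorded and a pre-dose Day 1 value of the same parameter exists, take the last pre-dose value as Baseline. Classify the timed post-dose value as post-baseline, eligible for PCI counts and worst-value shift tables. It would not enter the by-visit mean-change tables, because there is no post-dose Day 1 visit; the gain there is a correct Baseline for later visits.

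Keep the present day-level rule when a time is missing or no pre-dose Day 1 value exists. Under this part no subject loses Baseline or falls back to a Screening value.

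**SAP 10.3.** State that an SAE-related laboratory value drawn after the first dose on Day 1 cannot serve as Baseline, and that this takes precedence over the fallback above. In the unusual case where it was the only Day 1 value, Baseline would be the last earlier value if there is one. The existing exclusion in 10.3 already has that consequence.

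**Leave SAP 9.1 unchanged.**

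**Cost.** Two sentences in the SAP, one derivation condition in the analysis datasets, and no new data collection.

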## **10.2 Adverse Events**

Adverse events (AEs) will be summarized and presented using primary MedDRA System Organ Classes (SOCs) and preferred terms (PTs) according to the version of the MedDRA coding dictionary used for the study at the time of database lock. The actual version of the MedDRA coding dictionary used will be noted in the AE tables and in the clinical study report. Specific adverse events will be counted once for each subject for calculating percentages, unless stated otherwise. In addition, if the same adverse event occurs multiple times within a subject, the highest severity and level of relationship to investigational product will be reported.

### **10.2.1 Treatment-Emergent Adverse Events**

Treatment-emergent AEs are defined as any AE with the onset that is after the first dose of study drug and with an onset date no more than 5 half-lives of the study drug (i.e., 70 days). Events where the onset date is the same as the study drug start date are assumed to be treatment-emergent, unless the study drug start time and the AE start time are collected and the AE start time is prior to the study drug start time. All treatment-emergent AEs will be summarized overall, as well as by primary MedDRA SOC and Preferred Term. The SOCs will be presented in alphabetical order, and the PTs will be presented in alphabetical order within each SOC.

The number and percentage of subjects experiencing treatment-emergent AEs will be summarized.

### **10.2.2 Adverse Event Overview**

An overview of AEs will be presented consisting of the number and percentage of subjects experiencing at least one event for each of the following AE categories:

- Any treatment-emergent AE
- Any treatment-emergent AE related to study drug according to the investigator
- Any severe treatment-emergent AE
- Any serious treatment-emergent AE
- Any treatment-emergent AE leading to discontinuation of study drug
- Any treatment-emergent AE leading to death
- Adverse events of special interest (AESI, formerly known as safety topics of interest)
- All deaths
- Deaths occurring  $\leq 70$  days after last dose of study drug
- Deaths occurring  $> 70$  days after last dose of study drug.

An overview of treatment-emergent AEs per 100 patient-years of exposure will be presented by treatment group for the same AE categories listed above.

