5.6 Follow-Up After Subject Discontinuation of Study Drug or from Study

Discontinuation of Study Drug and Continuation of Study Participation

To minimize missing data for efficacy and safety assessments, subjects who prematurely discontinue study drug treatment should be encouraged to continue to be followed for all regularly scheduled visits (except for visits that are intended only for study drug administration [Weeks 6, 10, 14, 18, 22, 26, 30, 34, 38, 42, 46, and 50]), unless the subject has decided to discontinue the study participation entirely (withdrawal of informed consent). At the visits after study drug discontinuation, subjects should adhere to all study procedures except for dispensing of study drug and accountability, dosing diaries, and PK (conjugated ADC, total antibody, free A-1677770 assays) and immunogenicity (ADA assays) sample collection. Subjects should be advised on the continued scientific importance of their data even if they discontinue treatment with study drug early. Following discontinuation of study drug, the subject should be treated in accordance with the investigator's best clinical judgment irrespective of whether the subject decides to continue participation in the study.

If a subject prematurely discontinues study drug, the procedures outlined for the Premature Discontinuation Visit should be completed as soon as possible, preferably within 2 weeks, and preferably prior to initiation of another therapy.

In addition, a 30-day Follow-up Phone Call and 70-Day Follow-up Visit after the last dose of study drug is required to ensure all treatment-emergent AEs/SAE have been resolved. All attempts must be made to determine the date of the last study drug dose and the primary reason for discontinuation of study drug or study participation. This information will be recorded on the appropriate eCRF page. This Follow-up

Phone Call is not applicable for subjects who discontinued study drug prematurely and continued study participation with completion of at least 1 study visit that was at least 30 days after the last dose of study drug. This visit is not applicable for subjects who discontinued study drug prematurely and continued study participation with completion of at least 1 study visit that was at least 70 days after the last dose of study drug.

Premature Discontinuation of Study (Withdrawal of Informed Consent)

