7.5 Statistical Analyses for Safety

All safety analyses will be performed using the Safety Population, as defined in Section 7.2. Data will be analyzed based on the actual treatment subjects received. TEAEs, laboratory assessments, and vital signs will be summarized. Details will be described in the SAP.

A TEAE for the Safety Population is defined as an AE newly occurred or worsened after the first dose of study drug and within 70 days after the last dose of study drug. The number and percentage of subjects experiencing TEAEs will be tabulated using the Medical Dictionary for Regulatory Activities (MedDRA) system organ class and preferred term, by severity, and by relationship to the study drug as assessed by the investigator. Summaries (including percentages and events per 100 patient years) of SAEs, deaths, and AEs leading to discontinuation will also be provided. Pretreatment AEs will be summarized separately.

For selected laboratory parameters, a listing of all subjects with any laboratory value that is Grade ≥ 3 of NCI CTCAE will be provided. Mean change in laboratory and vital signs variables will be summarized. Additional details for the safety analysis are provided in the SAP.

[figure not shown]

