#### **10.2.4 Treatment-Emergent Adverse Events per Patient-Years of Exposure**

Exposure-adjusted AEs per 100 patient-years will be provided, where AEs per 100 patient-years of exposure are defined as the number of AEs divided by the total exposure in 100 patient-years. The study drug exposure is defined as the last dose date plus  $5 \times$  half-life (70 days), minus the first dose date.

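### The per-100-patient-years overview in SAP 10.2.2 includes death rows that fall wholly or partly outside the exposure time defined in SAP 10.2.4

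*SAP*

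**What the plan says.** SAP 10.2.2 sets out ten overview categories, to be shown as number and percentage of subjects. Most concern treatment-emergent events. The last three are all deaths, deaths up to 70 "days after last dose of study drug", and deaths more than 70 days after it. The section closes with a second request: "An overview of treatment-emergent AEs per 100 patient-years of exposure will be presented by treatment group for the same AE categories listed above".

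SAP 10.2.4 supplies the rate. It is "defined as the number of AEs divided by the total exposure in 100 patient-years". The denominator is fixed in the next sentence: "The study drug exposure is defined as the last dose date plus" five times the "half-life (70 days), minus the first dose date". The SAP gives no other person-time denominator for this table.

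SAP 10.2.1 limits treatment-emergent events to those "with an onset date no more than 5 half-lives of the study drug (i.e., 70 days"). Protocol 7.5 makes the anchor explicit: such an event "newly occurred or worsened after the first dose of study drug and within 70 days after the last dose of study drug".

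On follow-up, Protocol 5.6 says that "subjects who prematurely discontinue study drug treatment should be encouraged to continue to be followed for all regularly scheduled visits", unless they leave the study entirely. It also allows survival status to be sought from public records after withdrawal, where local rules permit.

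**The concern.** A rate per unit of person-time is meaningful when the events counted are those that could occur in the time counted. Here the later-death row opens on the day the denominator closes. Its rate relates deaths in one period to time in another, and the all-deaths row mixes the two periods.

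The row can be filled. A subject who stops study drug early may stay under observation well past day 70, and the SAP itself gives such deaths a row.

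The cost would be a mortality figure that looks exposure-adjusted but is not. Early stopping creates the time in which late deaths can be seen and also shortens the exposure denominator. A difference between arms in discontinuation alone could therefore look like a difference in mortality.

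**Working it through.** The plan states no figure for this rate, so there is nothing to reproduce. The check compares the two time windows and then illustrates the effect.

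**Windows**

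| Row in SAP 10.2.2 | Time in which the event can fall | Exposure in SAP 10.2.4 | Inside the denominator? |
|---|---|---|---|
| Deaths up to 70 days after last dose | first dose to last dose + 70 d | first dose to last dose + 70 d | yes |
| Deaths more than 70 days after last dose | after last dose + 70 d | same | none |
| All deaths | both periods | same | in part |

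The zero overlap in the second row follows from the definitions, whatever the data show.

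**Inputs from the documents:** 40 subjects per arm (SAP 2.4); last planned dose at Week 50 (Protocol 5.8); treatment period to Week 52, day 364.

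**Formula:** rate = 100 × events ÷ [sum of (last dose + 70 d − first dose) ÷ 365.25].

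1. A subject dosed to Week 50 contributes 350 + 70 = 420 days (1.15 patient-years). Forty such subjects give 46.0 patient-years. One later death would print as 100 ÷ 46.0 = 2.17 per 100, yet none of the 46.0 patient-years is time in which that death could fall.

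2. A subject whose last dose is at Week 10 leaves the denominator on day 70 + 70 = 140. From there to day 364 is 224 days of possible follow-up that earns no exposure. Planned visits leave such time only when the last dose comes before Week 42, since 42 × 7 + 70 = 364.

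3. Dependence on discontinuation. Assume that 10% or 30% of an arm of 40 take their last dose at Week 10, that all of these are followed to Week 52, and that the rest are dosed to Week 50.

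| | 10% stop (4) | 30% stop (12) |
|---|---|---|
| Exposure, days | 36×420 + 4×140 = 15,680 | 28×420 + 12×140 = 13,440 |
| Exposure, patient-years | 42.93 | 36.80 |
| Time after day 70, days | 4×224 = 896 | 12×224 = 2,688 |
| Time after day 70, patient-years | 2.45 | 7.36 |
| One later death, SAP rate per 100 | 2.33 | 2.72 |

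If the death hazard after day 70 is the same in both arms, expected later deaths are proportional to time after day 70. The ratio of expected printed rates is (2,688 ÷ 13,440) ÷ (896 ÷ 15,680) = 0.200 ÷ 0.0571 = 3.5. A factor of 3 comes from the extra late follow-up, and 15,680 ÷ 13,440 = 1.17 from the smaller denominator.

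4. All deaths on time in study. Adding the two periods gives 42.93 + 2.45 = 45.38 and 36.80 + 7.36 = 44.16 patient-years, ignoring the small loss of time from the death itself. One death is then 2.20 or 2.26 per 100, against 2.33 or 2.72 on the SAP denominator.

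**The case against.** The strongest reply is that the sentence speaks of treatment-emergent AEs and that SAP 10.2.4 sits under a treatment-emergent heading. Protocol 6.1 also stops general AE collection 70 days after study drug is discontinued. Read as a filter, those words leave the later-death row either always zero or limited to late deaths from an event that began inside the window.

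This shows a conflict in the wording, but it does not settle it. The sentence points to every category in a list that contains death rows not defined as treatment-emergent, and treatment-emergent AEs leading to death already have their own row. The SAP states neither filter rule, so two programmers could produce different tables. Even under the second rule, the death that defines the row still falls outside the denominator.

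The second reply is that little hangs on this. That stands. The same section already asks for number and percentage in each row, the summary is descriptive, and subjects who complete dosing have their follow-up visit about 70 days after the last dose. The row therefore mainly concerns early stoppers.

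A reader might infer more than the documents support in three respects:

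- **That all early stoppers are followed to Week 52.** They are encouraged to stay, not required to. The complete follow-up used above is an assumption.
- **That late deaths are divided only by other subjects' on-drug time.** The denominator includes the deceased subject's own exposure and every subject's 70 days off drug.
- **That the printed rate understates mortality many times over.** Such a multiple appears only when the death is divided by the short time after day 70, whose length is assumed. Neither counts nor a time-in-study rate would give it.

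**Conclusion.** The point holds as an inconsistency between two SAP sections. For deaths more than 70 days after last dose, the numerator lies wholly outside the denominator; for all deaths, partly so. Those two rates are not interpretable as printed and depend on how many subjects in each arm stop early and remain in follow-up. The row for deaths within 70 days does not have this mismatch.

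The size is small. Few or no late deaths are expected, no efficacy result or test is affected, and the planned counts and percentages are sound descriptions. The percentage of later deaths will also rise with the number of subjects observed past day 70, but it does not claim to adjust for time.

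The 3.5-fold ratio illustrates the direction of the distortion and does not predict it. It rests on assumed discontinuation of 10% and 30%, last doses at Week 10, complete follow-up and equal hazards. For all deaths, moving to time in study changes the illustrated rate only modestly.

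**What to change.** Amend the closing sentence of SAP 10.2.2 as follows:

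- Limit the exposure-adjusted overview to the treatment-emergent categories and deaths up to 70 days after last dose. The AESI row is not labelled treatment-emergent in the list; state that it stays and counts treatment-emergent events only.
- Report deaths more than 70 days after last dose as number and percentage only. Time in study would not suit this row alone, because most of that time precedes day 70.
- Report all deaths as number and percentage. If a rate is wanted, use 100 patient-years of time in study, from first dose to last contact or death, and label that denominator in the table.

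The cost is one SAP sentence and the matching table shell. No new data are needed.
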